10.3.3. Pruritus Numeric Rating Scale (NRS)

The Pruritus NRS is a scale to be used by the subjects to report the intensity of their pruritus (itch) during the last 24 hours. Peak pruritus (PP NRS) is an assessment of the maximum itch intensity in that Period while average pruritus (AP NRS) provides a measure of overall pruritus intensity.

Subjects will be asked the following question:

- For maximum itch intensity (PP NRS): “On a scale of 0 to 10, with 0 being ‘no itch’ and 10 being the ‘worst itch imaginable’, how would you rate your itch at the worst moment during the previous 24 hours?”
- For average itch intensity (AP NRS): “On a scale of 0 to 10, with 0 being ‘no itch’ and 10 being the ‘worst itch imaginable’, how would you rate your itch overall during the previous 24 hours?”

The screening PP/AP NRS will be determined by a single assessment using the PP/AP NRS (score ranging from 0 to 10) for the 24-hour Period immediately preceding the screening visit. The Baseline PP/AP NRS will be determined based on the average of daily PP/AP NRS (score ranging from 0 to 10) respectively during the 7 days immediately preceding Baseline (rounding to nearest whole number is not permitted). A minimum of 4 daily scores out of the 7 days immediately preceding Baseline is required for this calculation. PP/AP NRS at all follow-up visits will be determined in the same manner. Refer the details for the analysis visit window for diary data in Section 8.4. Subjects will receive instructions on how to record their PP/AP NRS scores and will complete the assessment once daily in the evening throughout the clinical study (including the run-in and the Follow-up Period).

In case of diary data, if the date of rescue therapy use is within the analysis visit window, the subject at the analysis visit will be treated as treatment failure except for OC analysis, and the weekly average will be imputed using the worst-case value for analysis

During Initial Period:

PP NRS will determined by an average as described above at every week from Baseline to Week 16 as a continuous variable for the Initial Period.

Descriptive summary of PP NRS will be provided for ITT and PP populations. Absolute change and percent change from Baseline for the PP NRS score will also be included in the summary.

AP NRS will determined by an average as described above at every week from Baseline to Week 16 as a continuous variable of the Initial Period. Descriptive summary of AP NRS will be provided for ITT population. Absolute change and percent change from Baseline for the AP NRS score will also be included in the summary.

Change from Baseline in PP NRS at each analysis visit up to Week 16 will be analyzed using ANCOVA, with missing values imputed using MI under MAR assumption, and MMRM. For the MI and MMRM analyses the least squares means (LSMeans), standard error of LSMean, and 95% CI for change from Baseline, as well as the difference in LSMean between the treatment groups, the two-sided 95% CI, and associated p-value will be presented. In addition, percent change from Baseline in PP NRS at each analysis visit up to Week 16 will be analyzed using MMRM.

Change from Baseline in percentage of itch-free days based on PP/AP NRS (score of 0 or 1) will also be summarized descriptively by visit.

This document is confidential.

1.0

CD14152.SPR118169.SAP.V01

Improvement in PP/AP NRS will be calculated using Baseline as the reference point for change in PP/AP NRS score. The proportion of subjects with PP NRS improvement ≥ 4 will be presented using OC, non-responder and LOCF. The proportion of subjects with an improvement of PP NRS ≥ 4 at Week 8 and Week 12, the proportion of subjects with a PP NRS < 2 at Week 1, Week 2, Week 8 and Week 12, the proportion of subjects with AP NRS ≥ 4 at each visit up to Week 16, and the proportion of subjects with AP NRS < 2 at each analysis visit up to Week 16 will be analyzed using non-responder imputation. The estimate of treatment unadjusted and strata-adjusted differences with the corresponding 2-sided 95% confidence intervals, and p-values from the Cochran-Mantel-Haenszel test will be presented.

Line plot for proportion of subjects with PP NRS improvement ≥ 4 and for proportion of subjects with PP NRS < 2 using Non-responder imputation will be presented for Initial Period on the ITT population.

"Itch-free days" will be defined if PP/AP NRS score is 0 or 1. The proportion of "itch-free days" will be calculated using 7 days diary data for the visit. A minimum of 4 daily scores out of the 7 days for the visit is required for the proportion calculation. The proportion of "itch-free days" will be calculated using number of days of PP/AP NRS score of 0 or 1 divided by number of days reported during the week. The summary of proportion of "itch-free days" based on PP NRS/AP NRS will be presented for Initial Period.

During Maintenance Period:

PP/AP NRS will determined by an average using 7 days data before the visit for Week 24, Week 32, Week 40, Week, Week 48 as a continuous variable for the Maintenance Period. Absolute change and percent change from Baseline and Maintenance Baseline (Week 16) for the PP/AP NRS score will also be included in the summary. No hypothesis testing will be performed.

Improvement in PP/AP NRS will be calculated using Baseline and Maintenance Baseline (Week 16) as the reference point for change in PP/AP NRS score. The proportion of subjects with an improvement of PP/AP NRS ≥ 4 and the proportion of subjects with a PP/AP NRS < 2 will be summarized.

For the subset of patients achieving an improvement of PP/AP NRS ≥ 4 at Week 16, the proportion of subjects achieved such an improvement at each analysis visit during the Maintenance Period will be summarized. For the subset of patients achieving a PP/AP NRS < 2 at Week 16, the proportion of subjects with PP/AP NRS < 2 at each visit during the Maintenance Period will be summarized using OC.

Line plot for proportion of subjects with PP NRS improvement ≥ 4 and for proportion of subjects with PP NRS < 2 using Non-responder imputation will be presented for Maintenance Period on the ITT population.

CCI

[figure not shown]
Approved 10-Nov-2022 00:00:00

This document is confidential.

Statistical Analysis Plan for Interventional Studies

Sponsor: Galderma Research & Development, LLC; Protocol No.: RD.06.SPR.118169

CCI

1.0

CD14152.SPR118169.SAP.V01

Approved 10-Nov-2022 00:00:00

[figure not shown]
This document is confidential.

CCI

1.0

[figure not shown]
CD14152.SPR118169.SAP.V01

Approved 10-Nov-2022 00:00:00

This document is confidential.

CCI

[figure not shown]
1.0

CD14152.SPR118169.SAP.V01

Approved 10-Nov-2022 00:00:00

This document is confidential.

CCI

[figure not shown]
1.0

CD14152.SPR118169.SAP.V01

Approved 10-Nov-2022 00:00:00

This document is confidential.

CCI

1.0

CD14152.SPR118169.SAP.V01

Approved 10-Nov-2022 00:00:00

[figure not shown]
This document is confidential.

CCI

1.0

CD14152.SPR118169.SAP.V01

Approved 10-Nov-2022 00:00:00

This document is confidential.

During Initial Period:

POEM will be collected at Baseline, Week 8, and Week 16 of the Initial Period. POEM total score will be summarized as a continuous variable using OC for ITT population. Absolute change from Baseline in POEM total score will also be summarized.

Change from Baseline in POEM total score at each visit up to Week 16 will be analyzed using ANCOVA, with missing values imputed using MI under MAR assumption. For the MI and MMRM analyses the least squares means (LSMeans), standard error of LSMeans, and 95% CI for change from Baseline, as well as the difference in LSMeans between the treatment groups, the two-sided 95% CI, and associated p-value will be presented.

During Maintenance Period:

POEM will be collected at Week 32, and Week 48 of the Maintenance Period. POEM total score will be summarized as a continuous variable using OC for ITT population. Absolute change from Baseline and Maintenance Baseline (Week 16) in POEM total score will also be summarized.

No hypothesis testing will be performed.

CCI

[figure not shown]
1.0

CD14152.SPR118169.SAP.V01

Approved 10-Nov-2022 00:00:00

This document is confidential.

CCI

[figure not shown]
1.0

CD14152.SPR118169.SAP.V01

Approved 10-Nov-2022 00:00:00

This document is confidential.

CCI

[figure not shown]
1.0

CD14152.SPR118169.SAP.V01

Approved 10-Nov-2022 00:00:00

This document is confidential.

CCI

1.0

CD14152.SPR118169.SAP.V01

Approved 10-Nov-2022 00:00:00

This document is confidential.

CCI

During Initial Period:

The number and percentage of subjects who used rescue therapy during Initial Period will be summarized by medication group (topical, phototherapy, systemic), category (for topical, systemic), preferred term and analysis visit and overall during the Initial Period.

In addition, the time (in days) to first rescue therapy use will be calculated during the Initial Period using Kaplan-Meier methodology by presenting the point estimates of the quartiles estimates with the corresponding 95% CI. Subjects who do not use any rescue therapy during Initial Period will be censored for the analysis and date of last visit of Initial Period will be used as the censoring date. Subjects who discontinued during Initial Period without intake of rescue therapy will also be censored as described above. Kaplan-Meier curve will also be provided.

During Maintenance Period:

The number and percentage of subjects who used rescue therapy during Maintenance Period will be summarized by medication group (topical, phototherapy, systemic), category (for topical, systemic), preferred term and analysis visit and overall during maintenance period.

In addition, the time (in days) to first rescue therapy from Week 16 will be calculated during the Maintenance Period. Kaplan-Meier estimates of time to first rescue therapy will be summarized. Subjects without such an event during Maintenance Period will be censored for the analysis and date of last visit of Maintenance Period will be used as the censoring date. Subjects who discontinued during Maintenance Period without intake of rescue therapy will also be censored as described above. Kaplan-Meier curve will also be provided.

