10.3. Secondary Efficacy Endpoints and Analysis

Secondary efficacy endpoints during Initial Period:

Secondary endpoints during Initial Period will be analyzed for both populations (Full population; Baseline PP NRS ≥ 7) on the ITT population.

If a subject received any rescue therapy, the data on or after receipt of rescue therapy will be considered as treatment failure.

Hypothesis testing of between group treatment differences will only be applied to endpoint variables. All other variables, e.g. IGA, will be summarized descriptively.

Binary endpoints will be analyzed using a Cochran-Mantel-Haenszel test adjusted for the randomized stratification variables (IGA severity [3=moderate, 4=severe] and PP NRS ≥ 7 , < 7] for full population; IGA severity only for Baseline PP NRS ≥ 7 population). Any subjects with missing data at respective Weeks will be regarded as a non-responder.

Analysis methods for continuous and QoL endpoints are listed in Table 10-1 below.

Continuous and QoL endpoints (change from Baseline to each visit) will be analyzed using an analysis of covariance (ANCOVA) including treatment group and randomization stratification variables as factors and appropriate Baseline values as a covariates, if applicable. Missing values will be imputed using MI under MAR assumption (see Appendix 22.1). The least squares means, estimated standard error, and 95% confidence interval (CI) for each endpoint will be presented for each treatment group and analysis visit. The estimated treatment difference for each endpoint at each analysis visit will be summarized by presenting the difference in least squares means between treatment groups, the two-sided 95% CI, and associated p-value. In addition, change from Baseline to each analysis visit in EASI, PP-NRS, CCI, CCI and percent change from Baseline in PP-NRS and CCI will be analyzed using a MMRM approach, including terms of treatment group, stratification variables, appropriate Baseline values, visit, and interactions between baseline score with visit and treatment group with visit. Kenward-Roger approximation will be used to estimate denominator degrees of freedom. An unstructured covariance will be used to model the within-patient errors in the analysis. If calculation within proc mixed for unstructured covariance not possible for "Type=UN" then use instead "Type=CS". A linear contrast will be used, within the MMRM framework, to estimate difference between nemolizumab and placebo. The least squares

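### SAP 10.3.3 words the Initial Period average-itch responder endpoint as a score of 4 or more, almost certainly a dropped reference to improvement; read literally, the tested event is unfavourable

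*SAP*

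**What the plan says.** SAP 10.3.3 builds AP NRS from a daily diary question, "how would you rate your itch overall during the previous 24 hours". Its anchors are 0 for no itch and 10 for the worst imaginable. A weekly average needs at least 4 of 7 daily scores.

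The Initial Period paragraph on responders opens with a rule for both scales: "Improvement in PP/AP NRS will be calculated using Baseline as the reference point for change in PP/AP NRS score". One sentence then lists four sets of proportions:

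- peak itch (PP NRS), change: "The proportion of subjects with an improvement of PP NRS ≥ 4 at Week 8 and Week 12";
- peak itch, score below 2 at Weeks 1, 2, 8 and 12;
- average itch: "the proportion of subjects with AP NRS ≥ 4 at each visit up to Week 16";
- average itch, score below 2 at each visit to Week 16.

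All of these "will be analyzed using non-responder imputation", with unadjusted and strata-adjusted differences, 95% confidence intervals and Cochran-Mantel-Haenszel p-values. SAP 10.3 adds: "Any subjects with missing data at respective Weeks will be regarded as a non-responder". It applies the secondary analyses to the full population and to subjects with baseline PP NRS of at least 7.

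For the Maintenance Period, SAP 10.3.3 has "The proportion of subjects with an improvement of PP/AP NRS ≥ 4", summarised without testing.

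On rescue, SAP 8.3 replaces data from the start of rescue with the worst possible score and also labels the subject a treatment failure. SAP 10.3.3 repeats this for diary weeks that contain the rescue date.

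**The concern.** Three of the four listed events are favourable. The average-itch item is a threshold on the score itself, in the direction of more itch. Non-responder imputation is conservative only when the event is a good outcome, because a missing subject is then denied the good outcome. When the event is a bad outcome, the same rule spares the missing subject the bad outcome.

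At stake is whether a set of tested comparisons, at every visit to Week 16 and in both populations, measures what it should. Programmed as written, benefit would appear as a negative difference beside endpoints where benefit is positive, and missing data would count in a subject's favour.

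**Working it through.** The documents give no rate, power or sample size for an AP NRS endpoint, so there is no figure to reproduce. The check compares the wording, then works through the scoring.

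**1. Wording.** The opening rule defines improvement for AP NRS against Baseline. In the visible Initial Period text, the natural responder use of that rule for average itch is the item with threshold 4, since a score below 2 needs no Baseline. The peak-itch item with the same threshold says improvement. The Maintenance text says improvement for both scales, and it also defines a subset who had achieved that improvement at Week 16. No unredacted passage gives the Initial Period average-itch item in that form.

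**2. A missing weekly score, read literally.**

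- For the item below 2, missing means non-responder, so the subject is treated as not below 2.
- For the item at 4 or more, missing means non-responder, so the subject is treated as not at 4 or more.

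The same missing value is therefore handled as if it lay from 2 up to, but not including, 4.

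**3. A rescue user, read literally.** The worst score is 10, and 10 ≥ 4, so the event is met. Treatment failure means non-responder, so the event is not met. The two instructions conflict.

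**4. The same cases with improvement of at least 4 as the event.** A missing subject is denied a favourable outcome, as intended. A rescue user has improvement = Baseline − 10, which is at most 0, so the worst score and the failure label agree.

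**5. Size of the scoring effect.** Let q be the share of observed subjects at 4 or more (assumed, 0.30 to 0.70). Let d be the missing share, taken as the 15% Initial Period dropout in the Protocol synopsis and 8.1.

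- Literal: q(1 − d)
- If missing counted as unfavourable: q(1 − d) + d

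| q | Literal | Missing unfavourable | Gap |
|---|---|---|---|
| 0.30 | 0.255 | 0.405 | 0.15 |
| 0.50 | 0.425 | 0.575 | 0.15 |
| 0.70 | 0.595 | 0.745 | 0.15 |

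The gap within an arm is d, whatever q is.

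**6. Effect on the treatment difference, equal missingness.** Assume q = 0.40 on nemolizumab and 0.60 on placebo, so the observed difference is −0.20.

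- Literal: 0.40 × 0.85 − 0.60 × 0.85 = 0.34 − 0.51 = −0.17.
- Missing unfavourable: (0.34 + 0.15) − (0.51 + 0.15) = −0.17.

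The difference is the same. The factor 0.85 would apply equally to the improvement endpoint.

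**7. Effect with unequal missingness (assumed rates).** Take q = 0.50 in both arms, with 10% missing on nemolizumab and 25% on placebo.

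- Literal: 0.50 × 0.90 − 0.50 × 0.75 = 0.450 − 0.375 = +0.075.
- Missing unfavourable: (0.450 + 0.10) − (0.375 + 0.25) = −0.075.

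The literal rule makes nemolizumab look worse although it lost fewer subjects. With the rates swapped, the literal difference is −0.075. In either case the arm losing more subjects looks better.

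At 500:250 the pooled proportion in the 10%/25% case is (0.450 × 500 + 0.375 × 250)/750 = 0.425. The standard error is √(0.425 × 0.575 × (1/500 + 1/250)) = 0.0383, and 1.96 × 0.0383 = 0.075. A difference of 0.075 sits at the two-sided 5% boundary, so the chance of p < 0.05 is about 50%. This is an unstratified approximation.

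**The case against.** The strongest reply is that this is a wording slip whose intent any careful programmer would recover. The opening rule, the parallel peak-itch item and the Maintenance text all point one way, and non-responder imputation makes sense only for a favourable event. The index of tables has a comparable slip in the other direction: the title of Table 14.2.2.2.9 speaks of improvement below 2 where the endpoint is a score below 2. The secondary endpoint lists and most secondary table titles are blacked out and may carry the right wording. All of this stands. It makes the point an editorial correction rather than a dispute over method, but it does not correct the operative sentence.

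A reader might infer four stronger things that the documents do not support:

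- **That the treatment effect is biased by 15 points.** Steps 5 and 6 show that 15% is a share of each arm scored on the wrong side. With equal missingness the difference is only attenuated. The documents give one overall dropout figure and none by arm.
- **That a reversed sign means a wrong conclusion.** A lower proportion with an unfavourable event is still benefit, and the mismatch would be conspicuous beside the item below 2 at the same visits.
- **That all dropouts are rewarded.** Protocol 8.5.1 asks subjects who stop study drug to keep attending visits and recording itch daily. Rescue users receive the worst score. The problem is confined to subjects whose diary data are truly missing.
- **That the main efficacy claims are affected.** The co-primary endpoints and the visible key secondary PP NRS endpoints are correctly worded in SAP 5.1, 5.2, 10.1.1 and 10.2.

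**Conclusion.** The point holds as a wording error in an operative rule. As written, the Initial Period average-itch item tests an unfavourable state, places truly missing subjects on the low-itch side, and gives rescue users two incompatible scores.

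The effect is limited. Only a secondary endpoint is involved, and SAP 10 does not adjust other secondary comparisons for multiplicity. With equal missingness, the difference shrinks by the factor 1 − d, as under any non-responder imputation. A spurious difference arises only if missingness differs between arms; the 7.5-point example rests on assumed rates of 10% and 25% and an assumed q of 0.50. Using 15% for d treats planned dropout as the missing share. Actual missing weekly scores could be lower, because subjects off drug stay in follow-up, or higher, because fewer than 4 diary days also gives a missing week.

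The conclusion about intent rests on the visible text. The redacted endpoint lists could confirm it but cannot be checked.

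**What to change.** In the Initial Period part of SAP 10.3.3, insert the words an improvement of before AP NRS ≥ 4 and add from Baseline after it, leaving the visit schedule unchanged. This makes the item match the paragraph's own rule and the Maintenance text. It also resolves the missing-data and rescue problems without any further rule.

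Then confirm that the secondary endpoint list, the AP NRS table titles and the programming specifications use the same definition. The title of Table 14.2.2.2.9 can be corrected in the same pass.

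The cost is a few words and a consistency check, with no change to data collection, sample size or any other analysis. It is best done before unblinding, so that the definition is not seen to change after results are known.

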10.3.24. Relapse during Maintenance Period

[figure not shown]
Relapse is defined as worsening of AD requiring rescue therapy, if judged to be medically necessary by the investigator (i.e., clinically significant worsening of signs and/or symptoms of AD). Relapse will be determine using AE, PR and CM data.

The number and percentage of subjects with relapse (worsening of AD requiring rescue therapy) will be summarized for the Maintenance Period using OC.

In addition, the time to first relapse from Week 16 will be calculated during the Maintenance Period using Kaplan-Meier methodology by presenting the point estimates of the quartiles estimates with the corresponding 95% CI. Subjects without such an event during Maintenance Period will be censored for the analysis and date of last visit of Maintenance Period will be used as the censoring date. Subjects who discontinued during Maintenance Period without relapse will also be censored as described above. Kaplan-Meier curve will also be provided.

This document is confidential.

CCI

[figure not shown]
1.0

CD14152.SPR118169.SAP.V01

Approved 10-Nov-2022 00:00:00

This document is confidential.

CCI

1.0

CD14152.SPR118169.SAP.V01

Approved 10-Nov-2022 00:00:00

This document is confidential.

13. Safety

All safety data will be summarized and listed on the Safety population.

Safety assessments will be conducted for all subjects at the screening visit (upon signing of the ICF) and at every subsequent visit. Safety will be assessed on the basis of AEs, unexpected adverse reactions, clinical laboratory data, vital signs, physical examination, respiratory examination, and ECG parameters. Summary of all safety endpoints will be presented by study Period (Initial Period, Maintenance Period, and Follow-up Period) for each treatment group.

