### 8.3.4 Removal of Subjects From Therapy or Assessments

Although the importance of completing the entire clinical study will be explained to the subjects, any subject is free to discontinue his/her participation in the study at any time and for whatever reason, specified or unspecified, and without any prejudice. No constraints are to be imposed on the subject, and when appropriate, a subject may be treated with other conventional therapy when clinically indicated. Investigators or the sponsor can also withdraw subjects from the clinical study if deemed to be necessary.

Reasons for discontinuing study drug include:

- Subject request (ie, consent withdrawal)
- Non-compliance with the study drug or study schedule
- Lost to follow-up
- Occurrence of AEs, including laboratory abnormalities, not compatible with the continuation of subject participation in the study, in the investigator's opinion, or unacceptable to the subject to continue, including but not limited to the following:
  - Serious immediate-type allergic manifestations including anaphylactic reaction
  - Serious worsening of asthma considered related to study drug administration
  - Diagnosis of a malignancy (except curatively treated in situ cervical carcinoma, squamous cell carcinoma [Bowen's disease] or basal cell carcinoma)
  - Opportunistic infections such as but not limited to active TB and other infections whose nature or course suggest an immune-compromised or immune-suppressed status
  - Any serious infection or any severe infection requiring treatment with parenteral antibiotics or oral antibiotics/antivirals/antifungals for > 2 weeks considered related to study drug administration
  - Confirmed or suspected COVID-19 infection (temporary discontinuation may be acceptable; for instructions on resuming study drug administration, see Section 8.3.4.2).

CONFIDENTIAL

- Pregnancy
- Use of non-permitted concurrent therapy (unless discussed and agreed upon with the investigator and medical monitor)
- Use of systemic rescue therapy, as specified in [Table 10](#) of Section [8.4.9.2](#) and Section [8.4.9.1.3](#)
- Treatment failure
- Investigator request
- Sponsor request, including any of the above criteria

The reason(s) for withdrawal will be documented in the CRF. Subjects who have been enrolled and treated will not be replaced by another subject.

Subjects who prematurely discontinue study drug will be encouraged to complete the scheduled study visits.

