### 8.5.1 Early Termination Visit

Subjects may discontinue from the study or discontinue the study treatment only and continue to participate in the study.

Subjects who prematurely discontinue from the study should undergo final study assessments according to the following guidelines:

- Subjects discontinued from the study during the initial treatment period on/before the Week 16 visit should attend an ET visit. A follow-up/final visit is required 12 weeks after the last study drug administration.
- Subjects discontinued from the study during the maintenance period should attend an ET visit.

A follow-up/final visit is required 12 weeks after the last study drug administration.

Subjects who prematurely discontinue the study drug will be asked to continue participation in the study and return for all remaining visits and assessments (including daily assessment of pruritus, sleep disturbance, etc). Participation will continue until the subject completes the final study visit or otherwise discontinues study participation.

Subjects requiring rescue medication (with or without study medication discontinuation) may be eligible for LTE study participation:

- Subjects requiring rescue medication during the initial treatment period should

CONFIDENTIAL

continue with study visits including the Visit 6/Week 16. A follow-up/final visit is not required for subjects participating in the LTE study.

- During the maintenance period, for subjects requiring rescue medication before the Week 32 visit, a wait period with continuing study visits until the Week 32 visit is due is required. Thereafter, no wait period is required. Subjects must complete the final study/ET assessments prior to rollover to the LTE study.

A follow-up visit is not required for subjects who will participate in the LTE.

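### Maintenance relapse counts only rescued worsening: exits for treatment failure without rescue are censored whatever the reason, and no sensitivity analysis is planned

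*SAP*

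**What the plan says.** **Event.** SAP 10.3.24: "Relapse is defined as worsening of AD requiring rescue therapy, if judged to be medically necessary by the investigator". AE, procedure and medication data are used to identify it. Worsening that does not lead to rescue is not an event.

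**Crude summary.** "The number and percentage of subjects with relapse (worsening of AD requiring rescue therapy) will be summarized for the Maintenance Period using OC". The section gives no denominator. The general table conventions (SAP 17.2.5.2) take subjects with an observation unless a table notes otherwise.

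**Time to relapse.** For subjects without an event, "date of last visit of Maintenance Period will be used as the censoring date", and "Subjects who discontinued during Maintenance Period without relapse will also be censored as described above". The stated Kaplan-Meier outputs are quartiles with 95% CIs and a curve.

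**Leaving treatment or study.** Protocol 8.3.4 lists "Treatment failure" as a reason for stopping study drug, in a separate item from systemic rescue. Protocol 8.5.1 adds: "Subjects who prematurely discontinue the study drug will be asked to continue participation in the study and return for all remaining visits and assessments". SAP 8.2, however, ends the Maintenance Period for an early discontinuer at the early termination date or 4 weeks after the last dose, whichever comes first.

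**Status.** SAP 10.3 makes all maintenance endpoints descriptive.

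**The concern.** Kaplan-Meier estimation assumes that a censored subject has the same later risk as those still under observation. A subject who leaves because AD has returned does not. That exit is close to the outcome itself, yet the rule treats it like a move to another city.

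Two groups are exposed: subjects who leave the study for treatment failure or AD worsening with no rescue recorded, and subjects who stop drug, stay in follow-up, and receive rescue only after SAP 8.2 has closed their Maintenance Period.

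The crude percentage does not repair this. Depending on how observed case is programmed, the subject counts as relapse-free or disappears. The visible text plans no composite, competing-risk or sensitivity analysis for relapse.

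At stake is the description of what happens when treatment is withdrawn or given less often. That belongs to the secondary objective of evaluating maintenance treatment (Protocol 7.3).

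**Working it through.** **1. The plan's own figure.** The only planning number behind this analysis is the expected maintenance sample (Protocol 8.1): 750 randomised 2:1 (500 and 250), 15% dropout, responder rates of 45% and 12%.

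- Nemolizumab: 500 × 0.85 × 0.45 = 191.25 (stated 190)
- Placebo: 250 × 0.85 × 0.12 = 25.5 (stated 26)
- Total: 216.75 (stated 216)

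It reproduces. Re-randomised 1:1:1, 190 / 3 gives about 63 per arm.

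**2. What is not given.** The documents state no relapse rate, no maintenance dropout rate and no exit reasons by arm. The rest is illustration with assumed inputs.

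**3. Formulas.** Let p be true 32-week relapse and f the share of relapsers who leave without rescue. Assume constant hazards.

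- Kaplan-Meier under the SAP rule: 1 − (1 − p)^(1−f)
- Crude, subject kept as relapse-free: (1 − f)p
- Crude, subject dropped: (1 − f)p / (1 − fp)
- Counting these exits as events: p

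**4. Assumed p = 45% in 1C and 15% in Q4W, a true difference of 30 points, with f equal in both arms.**

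| f | Kaplan-Meier 1C / Q4W (diff.) | Crude, kept (diff.) | Crude, dropped (diff.) |
|---|---|---|---|
| 10% | 41.6 / 13.6 (28.0) | 40.5 / 13.5 (27.0) | 42.4 / 13.7 (28.7) |
| 20% | 38.0 / 12.2 (25.8) | 36.0 / 12.0 (24.0) | 39.6 / 12.4 (27.2) |
| 30% | 34.2 / 10.8 (23.4) | 31.5 / 10.5 (21.0) | 36.4 / 11.0 (25.4) |

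For example, at f = 20%: 1 − 0.55^0.8 = 0.380 and 1 − 0.85^0.8 = 0.122. In an arm of 63 with p = 45%, this hides 63 × 0.45 × 0.20 = 5.7 relapses. The two crude readings differ by 3.2 points in the contrast (27.2 − 24.0) at the same f, so the unstated denominator matters in its own right.

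**5. Unequal shares.** With f = 30% in 1C and 10% in Q4W, Kaplan-Meier gives 34.2 − 13.6 = 20.6 points and crude (kept) 31.5 − 13.5 = 18 points. The direction is not guaranteed. Crude (kept), the difference is 0.30 − (0.45 × f in 1C − 0.15 × f in Q4W), so it shrinks only while f in Q4W is less than three times f in 1C.

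**6. Relative measures.** With equal f the hazard ratio is unchanged: ln(0.55) / ln(0.85) = 3.68 whatever f is. Only the absolute contrast moves.

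**7. Quartiles.** Where cumulative relapse stays below 25%, as in the assumed 15% arm, no quartile can be estimated. The crude percentage is then the only stated number beside the curve.

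**The case against.** The strongest reply is that few subjects are affected. Protocol 8.4.9.1.3 prefers topical rescue first with drug continued, and higher-potency topical steroid already counts as rescue, so many subjects stopping for treatment failure will already be events. That section and SAP 8.3 also use the term treatment failure for subjects who received rescue. Stopping drug is not leaving the study, and rescue later within the period still counts. Rescue is also a route to extension-study eligibility before Week 48, so leaving unrescued gives that route up. All this argues for a small f, and it stands. It does not make f zero. Before Week 32 the extension route carries a wait, and SAP 8.2 can close the period before a drug-stopper's rescue.

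The loss is also partly visible elsewhere. Maintenance IGA success and EASI responses are also shown with non-responder imputation, SAP 9.1 tabulates primary discontinuation reasons, and Figure 14.1.1.10 plots time to drug discontinuation by reason. That helps a careful reader but does not correct the relapse estimate. Much maintenance endpoint text is redacted, so another loss-of-response endpoint cannot be excluded.

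Two stronger inferences fail. A reader might infer that the hidden exits fall mostly in the withdrawal arm. No maintenance exit rates by arm are given, and the remark in Protocol 6.2.3 on more AD exacerbation with placebo comes from a parallel-group study, not a withdrawal design. A reader might also extend the point to time to first rescue, where "Subjects who discontinued during Maintenance Period without intake of rescue therapy will also be censored as described above". There the event is rescue use itself, so a non-user is not misclassified.

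**Conclusion.** The point holds as a limited one. Rescue is required for a relapse event, every other maintenance discontinuation is censored whatever the reason, and exit because AD has returned is informative. Both summaries can therefore understate relapse, and the crude one also has no stated denominator.

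The size is not known from the documents. The fall from 30 to about 28 to 23 points rests on assumed relapse of 45% and 15%, constant hazards and an equal unrescued share of 10% to 30%; the extension-study route points to the lower end of that share. If unrescued exits are more frequent in 1C, the absolute contrast shrinks. That is conservative for the efficacy of continued dosing, but it makes withdrawal look milder than it is.

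No hypothesis test, alpha or power is involved, so it would be wrong to read this as a threat to the trial's confirmatory conclusions. Nor do the documents show the sponsor's rescue-based definition to be wrong. What is missing is a check on how far the estimate depends on it.

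**What to change.** In SAP 10.3.24:

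1. Keep the rescue-based definition as the main version.
2. Add a supportive Kaplan-Meier analysis in which discontinuation of study drug or study with a recorded reason of treatment failure, lack of efficacy or AD worsening is an event on that date. Take the reason from the discontinuation record or AE data. The visible text does not show the CRF categories, so list the qualifying terms in the SAP.
3. Report the Kaplan-Meier relapse estimate at Week 48 with its 95% CI by arm, beside the crude percentage.
4. State the crude denominator and how a subject who leaves without relapse is counted.

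The cost is SAP wording, one derived flag, one extra table and a footnote explaining the broader definition. No change to planned data collection or clinical conduct is proposed.
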